Participants will be asked to complete a total of 3 surveys. Surveys will be administered via paper, online through an email link to the survey sent by Rutgers Population Science Datstat Illume Survey Software, or via phone with research staff. The baseline is administered when participants first enter the study, follow-up survey #1 is to be completed at the time of a post-op appointment, usually between 2-4 weeks after surgery and follow-up survey #2 is to be completed 6 months after the baseline survey. For both follow-ups, participants will be sent a link to the survey via email or they may also be contacted by telephone to complete the follow-up surveys. If requested, we can mail a copy of the follow-up survey to participants with a pre-paid envelope to return the survey. For follow-up #1 research staff will provide the participant with the follow-up survey at an appointment. The participant can complete the survey in clinic or they can take it home to return via mail in a pre-paid envelope. For patients who indicated a preference to complete the follow-up survey electronically, research staff will visit the participant at her appointment and remind her that the survey will be sent via email link. If patients take the survey home or prefer electronic surveys, staff will contact participants weekly and, if contact is not made within two weeks, the participant may be considered a survey refuser or drop. If participants skip the first follow-up survey, we will still send them the second follow-up survey at 6 months. We allow participants access to the website for the study duration. We do not anticipate that they will view the B-Sure website simply to look up answers for the follow-ups.

We will track website use to evaluate this possibility. Participants are paid \$25 for each survey they complete for a total of \$75. Rutgers Cancer Institute of New Jersey will provide payments to MSKCC participants in the form of gift cards which will require Rutgers staff to receive contact information (including names, address, email and phone #s) for MSKCC participants. MSKCC study consent will detail that Rutgers CINJ staff will receive their contact information to carry out study procedures. Research recruiters and site investigators [name], [name] and [name] will meet bi-weekly to review study accrual and troubleshoot enrollment challenges.

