3.2.3. Sample Size for RCT. We anticipate we will recruit participants for about 6months (months 17-22). Our goal is to enroll 90 to 130 women (65 in UC and 65 in CPM DA). We are anticipating a 70-75% acceptance rate based on our BRDA study. To obtain $N = 130$ (90 MSKCC, 10 CINJ, 30 MGH), we estimate approaching 169-182 women. Because acceptance rates are a study goal, this is only an estimate, and thus we allow 6-12 months for accrual.

3.2.4 Usual Care. Usual care consists of what traditionally occurs at both sites. At both sites, the surgical oncologist educates WSC regarding the facts about CPM, including the fact that it is not medically indicated, and does not reduce the risk of the spread of cancer. If interested, the patient is referred to a plastic surgeon.

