5.1. Primary Aim: Is the intervention trial feasible?

Approach and Analysis

For feasibility, 2 questions will be addressed: 1) Are patients joining/staying in the trial? We judge this study feasible if the participation rate (consented and complete baseline) is equal to or greater than 70% and the retention rate at follow-up is 85%. These "yardsticks" were selected to ensure there is sufficient interest to proceed to a larger scale trial. 2) Are participants using the DA in the way that was intended? We will evaluate log-ins, pages viewed, and how long modules are viewed. If participants review more than 75% of the pages, we will consider this acceptable usage. To evaluate the acceptability, we will

examine: whether participants use the DA, to what degree they use it, and factors predicting uptake and use. We will also look at whether patients 1) opened the web aid and 2) viewed each page. First, basic descriptive information will be gathered regarding participant log-ins and number and duration of log-ins. Second, DA evaluation and User Interface Satisfaction surveys will be examined.

We will judge the DA as acceptable if 75% of participants used it and if the average score was > 5.6/7 on the DA evaluation. *Using regression analyses, we will examine the following for association with DA use: younger age, internet familiarity, and higher education. The small sample (N = 40) and limited range of correlate categories limits options for statistical analyses. Missing values will be imputed from observed information (SAS Procedures MI and MIANALYZE). Confidence intervals and inferential procedures will adjust for uncertainty due to imputation.*

Table 1. Probability of declaring feasibility under various assumptions

Feasibility Component	Unaccept-able Rate	Acceptable Rate	Decision rule for claiming Feasibility	Prob. Declare Feasible under Unacceptable Rates	Prob. Declare Feasible under Acceptable Rates
Acceptance Rate	65%	70%	If 80 women recruited by the 114th (inclusive) approached	5%	96%
Completion Rate	79%	85%	If 68 participants complete survey	5%	96%

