Power. We expect to approach a maximum of 140 to enroll 100 women. If 100 women are enrolled in the study by the 140th patient approached and 85/100 participants complete the survey, then we will declare the study feasible. We chose the sample size and decision rules so that the probability of declaring feasibility would be approximately 5% under unacceptable rates of acceptance and completion and exceed 95% under acceptable rates. Power calculations are in **Table 1**. If the true acceptance and completion rates are 65% and 79%, respectively, which we consider to be too low to warrant further research, then the probability of declaring feasibility would be 5%. If the true acceptance and completion rates are 70% and 85%, respectively, which we consider large enough to warrant further research, then the probability of declaring feasibility would be 96%. These figures are based on binomial distributions

5.2. Secondary Aim 2: What is the impact of DA on CPM knowledge, psychosocial factors, decisional conflict, completeness of preparation, and CPM intention?

Approach and Analysis. Our outcomes are knowledge, perceived risk for recurrence, cancer worry, coping efficacy, anxiety, decisional conflict, preparedness, and intention. We anticipate that 100 women will complete the baseline and 85 will complete the follow-up. We will characterize the data using standard methods (means, medians, standard deviations, 95% confidence intervals) for the sample and separately by study arm. In exploratory analyses, we will use two sample repeated measures to compare outcomes using an intent-to-treat approach. We will assess associations among the outcome variables using Pearson's correlation coefficients. We will also characterize the patterns of missing data.

6. Reporting Results

The policies and procedures of Rutgers University's legal department (see: Investigator's Handbook) will govern publication of the results of this trial. The results of this trial will be submitted for publication in a timely manner following its conclusion. The Rutgers Cancer

Institute of New Jersey PI and all co-authors will review any abstract of manuscript prior to its submission.

7. Bibliography

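### The 96% chance of declaring feasibility does not follow from the stated binomial rules: at the acceptable rates each part passes about 40–58% of the time and both together about 22–31%.

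*Combined protocol and SAP*

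**What the plan says.** Feasibility is the primary aim. Section 5.1 gives the decision rule in three forms:

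- **Yardsticks (Approach and Analysis):** the study is feasible if the "participation rate (consented and complete baseline) is equal to or greater than 70% and the retention rate at follow-up is 85" per cent.
- **Table 1 of section 5.1:** acceptance passes "If 80 women recruited by the 114th (inclusive) approached"; completion passes "If 68 participants complete survey", with no denominator. Each row carries 5% at the unacceptable rate (65%, 79%) and 96% at the acceptable rate (70%, 85%).
- **Power paragraph:** "If 100 women are enrolled in the study by the 140th patient approached and 85/100 participants complete the survey", the study is declared feasible. The size and rules are said to have been chosen so that "the probability of declaring feasibility would be approximately 5% under unacceptable rates of acceptance and completion and exceed 95% under acceptable rates". For this two-part rule the paragraph then gives 5% at 65% and 79%. It adds that if the true rates are 70% and 85%, which it considers "large enough to warrant further research, then the probability of declaring feasibility would be 96" per cent. Both figures are said to be based on binomial distributions.

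Section 3.2.3 has a different target: "Our goal is to enroll 90 to 130 women". Section 3.2.2 has two follow-up surveys, one around the post-operative visit and another for which "follow-up survey #2 is to be completed 6 months after the baseline survey". Section 5.1 does not say which one counts as completion.

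**The concern.** A binomial count clears a cut-off placed at its own mean about half the time. Here 80/114 = 70.2%, 100/140 = 71.4%, 68/80 = 85% and 85/100 = 85%, against acceptable rates of 70% and 85%. A pass probability of 96% at those rates therefore cannot be right. The Power paragraph also gives a rule that needs both parts the same 96% that Table 1 gives each part alone, although a joint probability cannot exceed that of either part.

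The stake is how a negative result is read. If 96% were true, a verdict of not feasible would be strong evidence that participation or retention falls short of the acceptable rates, and a worthwhile larger trial could be dropped on that reading. The point concerns participation and retention only. Use and acceptability of the decision aid have their own criteria in section 5.1.

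**Working it through.** **Inputs (section 5.1).** Unacceptable rates 0.65 (acceptance) and 0.79 (completion); acceptable rates 0.70 and 0.85. Acceptance rules: at least 80 of 114 (Table 1), at least 100 of 140 (Power). Completion rules: at least 68, with 80 inferred as denominator from Table 1's acceptance row; at least 85 of 100 (Power).

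**Formula.** P(pass) = P(X ≥ k), X ~ Binomial(n, p). Both parts: the product of the two tails, assuming independence and completion judged among exactly 80 or 100 enrolled.

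**Attempt to reproduce 5% and 96%.**

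| Rule | At unacceptable rate | At acceptable rate |
|---|---|---|
| Plan, every row | 5% | 96% |
| Acceptance 80/114 | 14.4% | 53.0% |
| Acceptance 100/140 | 6.4% | 39.5% |
| Completion 68/80 | 11.6% | 57.6% |
| Completion 85/100 | 8.5% | 56.8% |
| Both, Table 1 counts | 0.1442 × 0.1163 = 1.7% | 0.5299 × 0.5762 = 30.5% |
| Both, Power counts | 0.0644 × 0.0847 = 0.5% | 0.3955 × 0.5683 = 22.5% |

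Neither stated figure is reproduced. On the unacceptable side the joint rule is conservative, so the material error is the 96%.

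**Could another reading rescue it?**

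- *Another denominator for the 68.* Holding the pass probability to 5% at 79% needs 78 or fewer participants (4.5%), and then only 36.4% pass at 85%. Reaching 96% at 85% needs 87 or more (96.9%), and then 63.5% pass at 79%. No denominator gives both.
- *Strict inequality.* Requiring one more success gives 33–46% per part at the acceptable rates.
- *Normal approximation.* With or without continuity correction it gives 36–56%.
- *Dependence.* Whatever the correlation, the joint probability cannot exceed the weaker part: 53.0% (Table 1) or 39.5% (Power).
- *Different cut-offs at the same size.* With 140 approached, at least 101 gives 4.4%/32.6% and at least 89 gives 67.4%/95.8%. With 100 enrolled, at least 87 gives 2.8%/34.7% and at least 79 gives 55.8%/96.1%. Reading approximately 5% loosely, at least 86 of 100 gives 5.0%/45.7%.

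**What would make 96% true?** The true rate at which each part passes 96% of the time is 76.8% (80/114), 77.4% (100/140), 90.4% (68/80) or 90.0% (85/100). These are 5 to 7 points above the rates the plan calls acceptable. The smallest designs with at most 5% and at least 95% for the plan's rate pairs are 960 approached (cut-off 649: 4.8%/95.0%) and 446 enrolled (cut-off 367: 4.8%/95.0%).

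**The case against.** The arithmetic is not in dispute; the best counter-arguments concern weight and scope.

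- *The rule looks harsh only at the minimum acceptable rates.* Section 3.2.3 anticipates 70–75% acceptance. At 75%, 80/114 passes 90.1% and 100/140 passes 85.8%. At 90% completion (an assumption; the plan does not project it), 85/100 passes 96.0%. This is fair, and the sponsor may prefer a strict rule. But the plan attaches 96% to 70% and 85%. Even at 75% acceptance with 85% completion, the joint chance under independence is 0.901 × 0.576 = 51.9% (Table 1) or 0.858 × 0.568 = 48.8% (Power).
- *The numbers depend on a sample size that section 3.2.3 contradicts.* True, so any replacement text must be tied to the rule chosen. The diagnosis does not change at 130: 130/182 passes 37.1% at 70%, and 111/130 passes 51.2% at 85%.
- *This is a pilot with descriptive yardsticks.* Safety, allocation, data collection and the observed rates are unaffected, and a reader can judge an observed 69% directly. That limits the damage to how the verdict is justified and interpreted. But that verdict is the primary aim's output, and the plan says the size and rules were chosen to deliver these probabilities.
- *Confidence intervals and the choice of follow-up survey are separate matters.* Agreed; they are secondary to the correction of 5% and 96%.

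**Conclusion.** The concern holds. The stated 96% is wrong for every version of the rule: 39.5–57.6% per part at the acceptable rates, and 22.5–30.5% for both. At exactly 70% and 85%, the study would be declared not feasible about 70–78% of the time (1 − 0.305 to 1 − 0.225).

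The joint figures assume independence; without it the ceiling is 53.0% or 39.5%. The Table 1 completion figure assumes a denominator of 80, but no other choice restores the stated pair. The acceptance rows and the 85/100 rule need neither assumption. Because this is the only power statement and it supports the primary aim, it must be corrected.

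**What to change.** 1. **State one rule.** Reconcile Table 1 (80/114 and 68), the Power paragraph (100/140 and 85/100), the yardsticks (at least 70%, and 85%) and the enrolment goal of 90 to 130 in section 3.2.3. Give both denominators, and say how completion is judged if enrolment is not 100. Also name the follow-up survey that counts as completion.

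2. **Replace 5% and 96%** in Table 1 and the Power paragraph with that rule's exact component and joint probabilities. If 100/140 with 85/100 is kept, for example:

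 > At true rates of 70% and 85%, the probability of meeting the acceptance criterion is 39.5%, the completion criterion 56.8%, and both (assuming independence) 22.5%; at 65% and 79% these are 6.4%, 8.5% and 0.5%.

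 If the 70% yardstick is kept instead, the acceptance cut-off is 98/140 (12.4%/54.2%). With completion judged as at least 85% of those actually enrolled, the joint chance is about 0.9%/29.5% with enrolment capped at 100, or 0.8%/28.0% uncapped. A different sample size needs its own figures.

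3. **Delete the statement that the probability exceeds 95% at the acceptable rates.** The sponsor should either keep the cut-offs and say that the rule is strict, ideally showing pass probabilities across 70–75% acceptance, or choose new cut-offs or rates and state their exact probabilities. The 960 approached and 446 enrolled needed for 5%/95% are outside a pilot.

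4. **Secondary:** report both observed rates with exact (Clopper-Pearson) 95% intervals beside the verdict. Treating the number approached as fixed, 98/140 gives 61.7% to 77.4%, 100/140 gives 63.2% to 78.7%, and 85/100 gives 76.5% to 91.4%.

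**Cost:** a table and wording correction plus one sponsor decision on the rule. No extra patients or visits. The downside is that the stated figures become less favourable.

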4.2. Follow-up Measures

4.2.1. Follow-up surveys (20m). All baseline measures except demographics will be given.

4.2.2. Process Evaluation: 1) *DA Evaluation* (DA arm only). Ratings include: extent that they used the DA, comprehensiveness of information, whether it presented material in a balanced manner, whether it influenced the decision, whether it was helpful in making the decision, whether it was helpful in understanding pros and cons, and whether they used the information in a discussion with the surgeon. Items are based on Brug (Brug et al., 2005) and previous research ([name] et al., 2010; [name] et al., 2005) 2) *DA implementation evaluation.* We will assess: a) log ins and time in DA; b) time spent in each module; c) number of pages printed out/sent to mobile device; d) ease of accessing and navigating the web-based application at home or at the center; 3) *User Interface Satisfaction* (Lund, 2001) assesses usefulness, ease of use, ease of learning and satisfaction with online tools. Feedback will be collected at the time of the first follow-up survey, but we may also contact participants by phone for a short debriefing on their experience with the site.

4.2.3 Risk and procedures for handling adverse events.

This study involves research presenting little risk. There are no physical risks or side effects associated with participation. If the participant is experiencing any psychological distress, as reported by the patient to the study staff, the study project coordinator will inform [name]. [name] will then determine if contacting the participant is necessary and/or helpful to evaluate distress levels and refer if further assistance is needed or requested. There are psychosocial resources available for patients. These procedures have been implemented successfully with our previous psychological intervention trials.

4.2.3.1. Adverse Events: In the proposed study, we define adverse events as psychological distress by the method outlined above, the following procedure for handling this event are: 1) the site PI will inform the IRB about the event; 2) the PI, [name], will be informed and this event will be reported to the Rutgers Cancer Institute of New Jersey IRB.

As with all research that collects protected health information, there is a risk that participants' confidentiality could be compromised during the study.

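### Section 5.2 compares the arms by repeated measures with no stated baseline covariate or contrast, although six of the eight listed outcomes are measured before randomisation

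*Combined protocol and SAP*

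**What the plan says.** Section 5.2 lists the outcomes: "Our outcomes are knowledge, perceived risk for recurrence, cancer worry, coping efficacy, anxiety, decisional conflict, preparedness, and intention". It gives the expected numbers: "We anticipate that 100 women will complete the baseline and 85 will complete the follow-up". The whole specification of the arm comparison is then one sentence, labelled exploratory: "we will use two sample repeated measures to compare outcomes using an intent-to-treat approach". No model, covariate, covariance structure, contrast or time point follows. The section also promises descriptive summaries with 95% confidence intervals by arm, correlations among outcomes, and a description of missing-data patterns.

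On the data available, section 3.2.2 states "Participants will be asked to complete a total of 3 surveys": baseline, one around the post-operative appointment (FU1), and one at 6 months (FU2). Assignment follows receipt of consent and the baseline survey. For the follow-ups, section 4.2.1 says "All baseline measures except demographics will be given". The measures table in section 4.1 schedules knowledge, risk perception, self-efficacy, preparation, decisional conflict and intention at all three surveys. Section 4 describes no measure for cancer worry or anxiety.

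**The concern.** The secondary aim is to supply preliminary effect data for a larger trial. With about 85 women followed up, the width of the intervals decides how useful those data are. A baseline value taken before randomisation is a valid covariate, and here it is already collected.

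Putting baseline into a model as a response is not the same as adjusting for it. A two-arm repeated-measures analysis over baseline, FU1 and FU2 offers two standard tests. The arm main effect averages in a visit at which no effect can exist, so it dilutes the effect. The arm-by-time contrast is in substance a change-score comparison. Both are less precise than adjustment at any correlation between 0 and 1, and section 5.2 does not say which would be reported. That also leaves the choice of test open until results are seen, across several outcomes and two follow-ups.

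**Working it through.** **No figure to reproduce.** Section 5.2 gives no effect size, SD, alpha, power or correlation for the arm comparison. The only probabilities in section 5 concern feasibility.

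**Inputs.** From section 5.2: 85 women at follow-up, taken as 42.5 per arm. Assumed: unit SD at each visit, the same correlation r between every pair of visits (compound symmetry), an equal effect d at FU1 and FU2, and complete data. r is shown at 0.3, 0.5 and 0.7. Matching section 5.2's outcome names to section 4's measures (for example coping efficacy to self-efficacy) is also an assumption.

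**Variance per woman of the estimate of d, for the FU1/FU2 average**
- Baseline as covariate: (1+r)/2 − r² = (1−r)(1+2r)/2
- Arm-by-time (follow-up mean minus baseline): (1+r)/2 + 1 − 2r = 3(1−r)/2
- Arm main effect over three visits: the mean has variance (1+2r)/3 but estimates 2d/3, so multiply by 9/4, giving 3(1+2r)/4
- Follow-ups only, baseline unused: (1+r)/2

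Loss = 1 − (adjusted variance)/(alternative variance). This gives 2(1−r)/3 for arm-by-time, (1+2r)/3 for the main effect and 2r²/(1+r) for follow-ups only.

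| r | Adjusted | Arm-by-time (loss) | Main effect (loss) | Follow-ups only (loss) |
|---|---|---|---|---|
| 0.3 | 0.56 | 1.05 (47%) | 1.20 (53%) | 0.65 (14%) |
| 0.5 | 0.50 | 0.75 (33%) | 1.50 (67%) | 0.75 (33%) |
| 0.7 | 0.36 | 0.45 (20%) | 1.80 (80%) | 0.85 (58%) |

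The arm-by-time and main-effect losses add up to 1: 2(1−r)/3 + (1+2r)/3 = 1. So at any r, one of these two tests discards at least half the information.

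**At a single visit.** Adjusted variance is 1 − r² and change-score variance is 2(1−r). The loss is (1−r)/2: 35%, 25% and 15% at r = 0.3, 0.5 and 0.7.

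**Common baseline mean.** A three-visit generalised least squares calculation that constrains the arms to the same baseline mean gives a per-visit variance of 1 − r² at every r tried (0.75 at r = 0.5). That equals adjustment, so the loss is 0%.

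**What this means for the intervals at r = 0.5.** Half-width = 1.96 × √(2 × variance/42.5).
- Follow-up average: adjusted 1.96 × √(2 × 0.50/42.5) = 0.30 SD; arm-by-time 1.96 × √(2 × 0.75/42.5) = 0.37 SD
- Single visit: adjusted 1.96 × √(2 × 0.75/42.5) = 0.37 SD; change score 1.96 × √(2 × 1.00/42.5) = 0.43 SD

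**The case against.** The strongest reply is that section 5.2 is silent rather than wrong. A reader might infer that the plan has chosen an unadjusted analysis, but the text does not say so. Its wording also allows follow-up responses with baseline as a covariate, or a model with a common baseline mean, which loses nothing. This stands: the fault is that baseline adjustment and the contrast are not specified. It does not remove the point, because nothing in the sentence implies either efficient form.

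A reader might also infer a loss of a third or more. The documents do not support a fixed figure. For the arm-by-time contrast on the follow-up average, the loss reaches a third only if r is 0.5 or lower. At a single visit it does so only if r is 0.33 or lower. No r is given.

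Nor is it established that women missing one survey would be dropped. That would follow from a classical repeated-measures ANOVA, which the plan does not name, and section 3.2.2 still sends FU2 to women who skip FU1. What is true is that the imputation text in section 5.1 is attached to the regression on decision-aid use, and section 5.2 does not say that it carries over.

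Finally, the comparison is labelled exploratory, the primary aim is feasibility, and no power is claimed. That limits the weight of the point. The conflict between the 100 women in section 5.2 and the 90 to 130 in section 3.2.3 changes the half-widths but not the percentage losses, which do not depend on sample size.

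**Conclusion.** The point holds as an improvement to an under-specified analysis. Section 5.2 neither names the baseline value as a covariate nor states the contrast, although six of the eight outcomes have a baseline taken before randomisation.

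The precision at stake runs from nothing (common baseline mean) to well over half (main effect including baseline). For the arm-by-time contrast on the follow-up average, which is a natural reading, it is 20% to 47% over r = 0.7 to 0.3. These figures rest on compound symmetry, equal effects at both follow-ups, complete data and an assumed r.

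The gain should be quoted for the quantity reported. At r = 0.5 the half-width of 0.30 SD applies to the follow-up average; at each visit it is 0.37 SD. The importance is modest, since the analysis is secondary and exploratory.

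**What to change.** Replace the sentence in section 5.2 with:

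*For each scale outcome measured at baseline and both follow-ups, a mixed model for repeated measures will be fitted with FU1 and FU2 as responses and baseline value, arm, visit and arm-by-visit as fixed effects. All randomised women with at least one follow-up contribute. The adjusted arm difference and its 95% CI will be reported averaged over FU1 and FU2 and at each visit.*

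Two matters need separate wording:
- **Intention.** Section 4.1.6 has intention rated only when no CPM decision has been made, and FU1 falls after surgery. Analyse the CPM decision or intention on its own, outside this model.
- **Cancer worry and anxiety.** The model can cover these only if section 4 identifies a measure taken at baseline and both follow-ups.

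The model leaves out women with no follow-up at all, so the intent-to-treat wording should state that.

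The cost is a few sentences of analysis text, with no new data and no change to the surveys.
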